- b) Any major illness/condition or evidence of an unstable clinical condition (eg, renal, hepatic, hematologic, gastrointestinal, endocrine, pulmonary, immunologic, psychiatric) or local active infection/infectious illness that, as determined by medical judgment, will substantially increase the risk to the subject if he or she participates in the study
- c) Any major surgery within the last 30 days before the first dose of study treatment, or any surgery planned during the course of the study
- d) Cancer or history of cancer or lymphoproliferative disease within the previous 5 years (other than adequately treated cutaneous basal cell or squamous cell carcinoma with no evidence of recurrence)
- e) Class III or IV congestive heart failure as defined by the New York Heart Association (NYHA) or any recent onset of heart failure resulting in NYHA Class III/IV symptoms
- f) Acute coronary syndrome (eg, myocardial infarction, unstable angina pectoris) and/or any history of significant cerebrovascular disease within 24 weeks before screening
- g) Current or recent (within 3 months before randomization) gastrointestinal disease, including gastrointestinal surgery, that could impact the absorption of study treatment
- h) Subject with non-SLE concomitant illness, as determined by medical judgment, who is likely to require additional systemic glucocorticosteroid therapy during the study (eg, asthma).
- i) Significant blood loss (> 500 mL) or blood transfusion within 4 weeks before randomization
- j) Inability to take medication orally
- k) Inability to undergo venipuncture and/or tolerate venous access
- l) Recent (within 6 months before randomization) drug or alcohol abuse as defined by the Diagnostic Criteria for Drug and Alcohol Abuse in the Diagnostic and Statistical Manual of Mental Disorders IV ([APPENDIX 8](#))
- m) Any other sound medical, psychiatric, and/or social reason as determined by medical judgment

3) Prior and Concomitant Therapy

- a) Inability to comply with restrictions and prohibited treatments ([Section 6.7.1](#)); inability to comply with discontinuation requirements listed in [APPENDIX 7](#)
- b) Taking more than 1 immunosuppressant
- c) Prior exposure to TYK2 inhibitors
- d) Prior exposure to anifrolumab, rontalizumab, ustekinumab, or interferon alpha kinoid (INF α Kinoid)
- e) Current administration of opioids unless all the following criteria are met:
 - i) The prescribed dose has been stable for ≥ 4 weeks before screening

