6.7.1 Prohibited and/or Restricted Treatments

Restrictions and prohibitions on prior and concomitant medications are as follows:

1. Prior exposure to BMS-986165 or other TYK2 inhibitors is prohibited.
2. Rescue therapy other than prednisone or equivalent is prohibited.

3. Use of intramuscular, intra-articular, intrabursal, and IV CS is prohibited (Inclusion Criterion 3)b); [Section 5.1](#)). Initiation during the study of short-term treatment with inhaled CS for a nonlupus medical condition must be discussed with the [REDACTED] medical monitor. Topical CS use may not be initiated during treatment. Modified-release CS formulations are prohibited.
4. Topical NSAID use may not be initiated during treatment. No more than 1 oral NSAID may be used during the study. Aspirin is allowed (in addition to a single NSAID and topical NSAIDs) at stable doses no higher than 325 mg/day throughout the study. NSAIDs may not be used on an as-needed basis. Although regimens are required to be stable throughout the study, NSAID dosing may be decreased or discontinued if due to NSAID toxicity. Adjustments in NSAID regimens must be discussed with the [REDACTED] medical monitor.
5. Use of opioid analgesics is prohibited unless criteria outlined in Exclusion Criterion 3)e); [Section 5.2](#), are met.
6. Use of cyclophosphamide (including ophthalmic) or any IV, intrabursal, intratendinous sheath, intramuscular, subcutaneous, intra-articular, or biologic agent is prohibited. Required discontinuation periods for immunomodulatory and biologic drugs before the signing of informed consent are provided in [APPENDIX 7](#). For similar agents not listed, the discontinuation period is 4 weeks or 5 half-lives, whichever is longer, and must be discussed with the [REDACTED] medical monitor.
7. Live vaccines are prohibited during the TP or within the 2 months after the last dose. Heat-killed or otherwise inactivated or protein vaccines such as influenza and pneumococcal vaccines may be received at any time on study. Any other inactivated vaccines (eg, tetanus, etc) should be used according to local guidelines during the TP (Exclusion Criterion 4)g); [Section 5.2](#)).
8. Exposure to any investigational drug or placebo within 12 weeks or 5 half-lives (whichever is longer) before screening is prohibited (Exclusion Criterion 3)f); [Section 5.2](#)

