9.3.1.2 Nonresponders

Subjects will be considered nonresponders in the TP for the responder-type efficacy endpoints (ie, BICLA and SRI) in the primary and secondary analyses at weeks 32 and 48, respectively, if they meet any of the following criteria:

- Requires CS dose > 7.5 mg/day prednisone or equivalent after Week 20
- Requires CS rescue therapy beginning after the Week 8 visit
- Requires more than 1 burst of CS rescue therapy
- Requires dose increase in background immunosuppressant or antimalarial medication
- Requires treatment with medications prohibited by the protocol ([Section 6.7.1](#) and [APPENDIX 7](#))
- Discontinues treatment before the assessment timepoint or has a missing value for the particular endpoint

Nonresponder definitions for other time points will be provided in the SAP.

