 - Oral steroid burst for non-SLE indication is permitted up to week 24 or between week 32 and week 40
- Initiation of or increases in oral NSAIDs (compared to baseline) occurring within the 7 days before the W32 assessment timepoint
- Initiation of or increase in immunosuppressant dosage/regimen and/or antimalarial dosage/regimen (compared to baseline)
 - Dose decrease or discontinuation is permitted
 - Discontinuation with subsequent restart at the same or lower dose is permitted
 - Immunosuppressants are defined as (combinations of these are not permitted): Azathioprine, 6-MP, methotrexate, leflunomide, MMF
 - Antimalarials are defined as: chloroquine, hydroxychloroquine, or quinacrine
- Subjects takes any medications included in protocol Appendix 7 between first dose date and efficacy assessment visit
- Permanent treatment discontinuation of IP before the considered time point
- Missing value for the endpoint at the considered time point
- Subjects who are lost to follow-up or discontinue the study early are considered non-responders for all time points at and after loss to follow up or study discontinuation

Primary Analysis

The primary analysis will be conducted on the randomized population.

The analysis of NRI-imputed SRI(4) response at Week 32 will be conducted using logistic regression modeling, with treatment group (four levels) and redefined stratification factor (see [section 6.5](#), thirteen levels) as fixed factors. The odds ratios of response will be estimated and tested between the BMS-986165 treatment groups and the placebo group [REDACTED]. In case the logistic regression model fit is not stable the region stratification factor may be removed from the model (resulting in 5 stratification factors: non-Japan subjects with baseline CS dose ≥ 10 mg/day and SLEDAI-2K score ≥ 10 , non-Japan subjects with baseline CS dose < 10 mg/day and SLEDAI-2K score ≥ 10 , non-Japan subjects with CS dose ≥ 10 mg/day and SLEDAI-2K score < 10 , non-Japan subjects with CS dose < 10 mg/day and SLEDAI-2K score < 10 and Japan subjects). Estimated odds ratios of response with corresponding 2-sided 95% confidence interval (CI) and p-value will be reported.

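### The SAP's closed non-responder list for SRI and BICLA omits treatments that the protocol counts as failure, notably biologics not named in Appendix 7

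*SAP*

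**What the plan says.** **Protocol.** Section 9.3.1.2 lists the conditions that make a subject a non-responder for the responder-type endpoints, which it gives as BICLA and SRI, at Weeks 32 and 48. One condition is "Requires treatment with medications prohibited by the protocol", with a reference to Section 6.7.1 and Appendix 7 and no look-back window. The section then adds "Nonresponder definitions for other time points will be provided in the SAP", so the Week 32 and Week 48 rules are fixed in the protocol itself.

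Four items of Section 6.7.1 matter here:
- Item 2 bars rescue therapy other than prednisone or equivalent.
- Item 4: "Topical NSAID use may not be initiated during treatment".
- Item 5: "Use of opioid analgesics is prohibited unless criteria outlined in Exclusion Criterion 3)e". One of those criteria is "The prescribed dose has been stable for ≥ 4 weeks before screening", which an opioid first started on study cannot meet.
- Item 6 ends its list of barred agents with "intramuscular, subcutaneous, intra-articular, or biologic agent is prohibited". It goes on to deal with similar agents that Appendix 7 does not list, so the protocol does not treat that table as exhaustive.

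**SAP.** Section 11.7.1 gives a closed list of prohibited medications that trigger non-responder imputation. It covers corticosteroid items, oral NSAIDs started or increased in the 7 days before Week 32, five immunosuppressants, three antimalarials, and finally "Subjects takes any medications included in protocol Appendix 7 between first dose date and efficacy assessment visit". The BICLA list in 11.7.2.2 follows the same pattern.

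**The concern.** The protocol defines failure by reference to everything it prohibits. The SAP defines it by enumeration, and the enumeration is shorter. A subject whose disease is treated with a prohibited agent that is on neither the SAP list nor Appendix 7 can be credited as a responder to the assigned arm. This affects the primary endpoint (SRI(4) at Week 32) and two secondary endpoints (SRI(4) and BICLA at Week 48).

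Two things are at stake. One is whether the primary analysis estimates the response that the protocol defines. The other is whether response on a prohibited SLE rescue drug is attributed to study treatment or placebo.

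**Working it through.** This is a comparison of definitions. The only power figure in the documents (at least 84% for a 20-point difference, protocol 9.1 and SAP 5.1) does not bear on it, and the placebo rate behind that figure is not visible.

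**Step 1. Prohibition against list.**

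| Protocol 6.7.1 | Entry in SAP 11.7.1 / 11.7.2.2 |
|---|---|
| Any biologic agent (item 6); rescue other than prednisone (item 2) | Only agents named in Appendix 7, plus the listed immunosuppressants and antimalarials |
| Opioids not meeting Exclusion 3)e) (item 5) | None |
| Topical NSAID started on treatment (item 4) | None; NSAID entry is oral only |

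**Step 2. Is the biologic gap real?** Exclusion 3)d) names "Prior exposure to anifrolumab, rontalizumab, ustekinumab, or interferon alpha kinoid". None of these four is in the Appendix 7 table. Agents that the protocol itself mentions therefore fall outside the SAP's trigger.

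**Step 3. One subject through both rules.** Suppose a subject starts ustekinumab at Week 16, stays on investigational product, keeps prednisone at or below 7.5 mg/day after Week 20, has no corticosteroid burst and meets all three SRI(4) components at Week 32.
- Protocol 9.3.1.2: non-responder, because 6.7.1 items 2 and 6 prohibit the drug.
- SAP 11.7.1: no trigger applies, so responder.

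**Step 4. Does another planned analysis apply the full rule?** None that is visible.
- Sensitivity analysis #1 imputes failure only for missing values.
- Sensitivity analysis #2 drops the medication restrictions altogether.
- The tipping-point analysis varies only imputed values, so this subject never enters it.
- The per-protocol analysis was removed (SAP 5.4.2).
- The medication deviations in SAP Appendix 5 point back to the 11.7.1 list and Appendix 7.

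**Step 5. Size per subject.** With about 90 per arm (protocol 9.1), 1/90 = 1.1 percentage points. For illustration only, assume 36/90 = 40% on placebo and 54/90 = 60% on active, a difference of 20.0 points:
- two extra placebo responders: 38/90 = 42.2%, difference 17.8 points;
- two extra active responders: 56/90 = 62.2%, difference 22.2 points;
- two extra in each arm: 62.2% − 42.2% = 20.0 points, unchanged.

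**Step 6. The Appendix 7 bullet itself.** Appendix 7 lists leflunomide (36 weeks). Inclusion Criterion 3)a) permits leflunomide as background therapy, and SAP 11.7.1 names it among the immunosuppressants for which only initiation or an increase counts. Read literally, the Appendix 7 bullet makes every background leflunomide user a non-responder. The protocol rule has the same conflict, because it also cites Appendix 7.

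**The case against.** **The SAP had to make 6.7.1 programmable, and the change is disclosed.** Item 6 literally bars agents by route (intravenous, subcutaneous and others), which cannot sensibly be coded as failure, and some items of 6.7.1 are entry rules. Protocol 9.3 leaves detailed specifications to the SAP, and SAP 5.4.2 records that the list of prohibited medications was refined, before any analysis. This stands in part: it is not a hidden change, and some interpretation was needed. But the log neither names nor explains these omissions, and 9.3.1.2 hands only other time points to the SAP.

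**The biologic gap is narrow.** Belimumab, rituximab, abatacept and tocilizumab are in Appendix 7, and Exclusion 3)d) concerns prior exposure, not likely use on study. Some affected subjects would also fail on corticosteroid or discontinuation rules. This limits the likely size of the effect but does not remove the conflict.

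**Some text cannot be seen.** Protocol text after 6.7.3 and SAP Appendix 4 are redacted, and the WHO Drug term list is not shown. The visible imputation text refers to none of them for further medications.

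Three stronger readings are tempting and are not supported:
- *That the omission biases the result against the drug.* A reader might expect extra treatment to be commoner on placebo. The documents give no frequency of use by arm, and Step 5 shows that the difference could shrink, grow or stay the same.
- *That a late opioid creates SRI(4) responders.* Week 30 is 14 days before Week 32. SLEDAI-2K scores a finding present at the visit or in the last 30 days, so arthritis present before a Week 30 opioid is still scored. BILAG and the physician's global assessment look back 4 weeks and 30 days (SAP 6.1). Such a subject would be classified differently by the two rules, but the opioid would not have produced the 4-point fall.
- *That the joint-count analysis departs from the protocol.* SAP 11.7.2.5 does use the 11.7.1 criteria to set values to missing. Protocol 9.3.1.2 covers only responder-type endpoints, so there is no protocol rule there to depart from.

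**Conclusion.** The concern holds as a conflict of definitions. For SRI at Weeks 32 and 48 and BICLA at Week 48, the SAP's list is narrower than the protocol's rule, without a stated reason, and no visible analysis applies the protocol's rule in full. The clearest case is a biologic or other prohibited SLE rescue therapy not named in Appendix 7, because the subject can be counted as a responder while on it. New opioids and new topical NSAIDs are omitted in the same way, but the documents do not show that they would produce response.

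The size is 1.1 points of an arm's rate per reclassified subject, assuming 90 per arm. The total effect and its direction cannot be derived from the documents.

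**What to change.** Before unblinding:

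1. In SAP 11.7.1 and 11.7.2.2, widen the Appendix 7 bullet to: *any medication in protocol Appendix 7, and any biologic or other SLE therapy prohibited by protocol 6.7.1, whether or not named in Appendix 7*. Build the WHO Drug term list to match, and say how the route-based wording of 6.7.1 item 6 is read.
2. For newly started or increased opioids and newly started topical NSAIDs, choose one of two courses. Either add them with no look-back window, as in the protocol rule, or state why they are left out and add a sensitivity analysis that applies the full rule of 6.7.1 plus Appendix 7. Borrowing the 7-day oral NSAID window would itself depart from 9.3.1.2.
3. Reconcile Inclusion Criterion 3)a), Appendix 7 and the SAP list on leflunomide, so that its status in the non-responder rule is unambiguous.

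These edits concern how outcomes are counted, not what subjects may be given. Concomitant medications are already collected (protocol 6.7), so the cost is SAP wording and some extra drug coding. Response rates may fall slightly.

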5 STUDY POPULATION

Eligibility criteria for this study have been carefully considered to ensure the safety of the study subjects and that the results of the study can be used. It is imperative that subjects fully meet all eligibility criteria.

All screening and randomization evaluations must be completed and reviewed to confirm that potential subjects meet all eligibility criteria. The investigator will maintain a screening log to record details of all subjects screened and to confirm eligibility or record reasons for screening failure, as applicable. CRS and the PRA medical monitor will review all eligibility criteria for all subjects who are not initially screen-failed by the site. Study designated therapeutic experts outside of the Sponsor and CRO may review eligibility criteria as needed. No subject will be randomized without confirmation of eligibility by CRS and the PRA medical monitor. In addition, [REDACTED] will assign BILAG grades for all subjects based on information provided by the sites. Procedures conducted as part of the subject's routine clinical management and obtained before signing of informed consent may be utilized for screening purposes, provided the procedure meets the protocol-defined criteria and has been performed within the timeframe defined in the Schedules of Activities ([Section 1.3](#)). However, all laboratory testing must be performed by the study-specific central laboratory.

The duration of the screening period (SP) is up to 4 weeks. If eligibility parameters cannot be obtained within this time period, the SP may be extended by up to 5 days if approved by the [REDACTED] medical monitor. Rules for retesting and rescreening are provided in [Section 5.5](#).

To be eligible for the study, subjects must meet the criteria in Section 5.1. To be randomized into the study on Day 1, subjects must meet the criteria in [Section 5.3](#).

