5.1 Inclusion Criteria

In order to be eligible to participate in this study, an individual must meet all of the following criteria:

1) Signed Written Informed Consent

[figure not shown]
- a) Willing to participate in the study and have the ability to give informed consent
- b) Willing and able to complete all study-specific procedures and visits

2) SLE Disease Characteristics

- a) Diagnosed ≥ 24 weeks before the screening visit
- b) Meets the Systemic Lupus International Collaborating Clinics (SLICC) classification criteria for SLE⁹ [APPENDIX 5](#)
- c) One of the following: elevated antinuclear antibodies (ANA) $\geq 1:80$ or positive anti-dsDNA (positive includes indeterminate results) or positive anti-Smith (anti-Sm) as determined by the central laboratory
- d) Total SLEDAI-2K score ≥ 6 points and clinical SLEDAI-2K score ≥ 4 points with joint involvement and/or rash (score must be confirmed by CRS)
 - i) Lupus headache, alopecia, organic brain syndrome, and mucosal ulcers cannot count toward the points required for screening at entry.
 - ii) Clinical SLEDAI-2K excludes laboratory abnormalities such as hematuria, pyuria, urinary casts, proteinuria, positive anti-dsDNA, decreased complement, thrombocytopenia, and leukopenia.
- e) At least 1 of the following BILAG-based protocol-specific manifestations of SLE [REDACTED]:

- i) BILAG A or B grade in the Mucocutaneous body system. [REDACTED]

- ii) Modified BILAG A or B score in the Musculoskeletal body system [REDACTED]

iii) If only 1 B and no A grade is present in the Mucocutaneous body system or in the Musculoskeletal body system due to arthritis, then at least 1 B grade must be present in one of the other body systems, for a total of 2 BILAG B body system grades.

3) Medications for SLE

- a) Background therapy is required for ≥ 12 weeks before the screening visit and must be at a stable dose for ≥ 8 weeks before the screening visit and remain stable until randomization and throughout study participation. Details for specific medications are as follows:
- Immunosuppressants (combinations of these are NOT permitted):
 - azathioprine (maximum 200 mg/day)
 - 6-mercaptopurine (6-MP)
 - methotrexate (MTX; maximum 25 mg/week; dose and route of administration of MTX may not be changed for 8 weeks before the screening visit and throughout study participation)
 - leflunomide

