 - mycophenolate mofetil/mycophenolic acid (MMF). **Note:** Subjects who are receiving MMF may participate in the study only if administered as a maintenance therapy and up to a maximum of 2 g/day (or equivalent); in subjects

of African ancestry, 3 g/day (or equivalent) is acceptable. Treatment may be interrupted due to neutropenia per the product label.

- Antimalarials: chloroquine, hydroxychloroquine, or quinacrine; monotherapy is permitted if the minimum doses are met: chloroquine 125 mg QD, hydroxychloroquine 200 mg QD, or quinacrine 100 mg QD
 - Required discontinuation periods for other immunomodulatory drugs (eg, cyclosporine, tacrolimus, etc) or biologic drugs (eg, rituximab, belimumab, tocilizumab, etc) are provided in [APPENDIX 7](#). If a drug is not specifically listed, consult the [REDACTED] medical monitor for guidance. Usual discontinuation periods are 4 weeks or 5 half-lives, whichever is longer.
- b) CS (prednisone or equivalent) background therapy is permitted but not required. For subjects taking CS, the dose must be stable for ≥ 2 weeks before the screening visit, cannot exceed 30 mg/day at screening, and must remain stable until randomization. CS monotherapy is not permitted. Prednisone equivalents are provided in [APPENDIX 6](#).

- c) Requirements for subjects who are receiving chronic therapy with nonsteroidal anti-inflammatory drugs (NSAIDs; including marketed cyclooxygenase-2 inhibitors) are as follows; exceptions or changes may be possible with approval by the [REDACTED] medical monitor:
- Doses must be stable for 14 days before the screening visit and must remain stable until randomization and throughout the study.
 - No more than 1 oral NSAID may be used (at a stable dose) during the study and may be combined with topical NSAIDs.
 - Use of 1 or more topical NSAIDs is permitted but must follow a stable regimen throughout the study.
 - Aspirin is allowed (in addition to a single NSAID and topical NSAIDs) at stable doses no higher than 325 mg/day throughout the study.

4) Age and Reproductive Status

- a) Men and women aged 18 to 75 years inclusive at the time of screening
- b) Women of childbearing potential (WOCBP) must have a negative serum or urine pregnancy test (minimum sensitivity 25 IU/L or equivalent units of beta-human chorionic gonadotropin [β -HCG]) within 24 hours prior to the start of study treatment.
- c) Women must not be breastfeeding.

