6 TREATMENT

Study treatment is defined as any investigational treatment(s), marketed product(s), placebo, or medical device intended to be administered to a study subject according to the study randomization or treatment allocation

Study treatment includes both investigational [medicinal] product (IP/IMP) and noninvestigational [medicinal] product (non-IP/non-IMP) and can consist of BMS-986165 and placebo. Information about the pharmacology and previous experience with BMS-986165 is provided in [Section 2.2](#).

An IP, also known as IMP in some regions, is defined as a pharmaceutical form of an active substance or placebo being tested or used as a reference in a clinical study, including products already with a marketing authorization but used or assembled (formulated or packaged) differently than the authorized form, or used for an unauthorized indication, or when used to gain further information about the authorized form.

Other medications used as support or escape medication for preventative, diagnostic, or therapeutic reasons, as components of the standard of care for a given diagnosis, may be considered as noninvestigational products. [Table 5](#) shows the study treatments for Protocol IM011021.

Table 5: Study Treatments for IM011021

| Product Description/Class and Dosage Form | Potency | IP/Non-IP | Blinded/Open-Label | Packaging/Appearance | Storage Conditions (per label) | Comments |
|---|-----------------------------|-----------|--------------------|--|--|--|
| BMS-986165 oral capsule | (as the free base) | IP | Blinded | Blister card containing 64 active (3 mg BMS 986165) and/or placebo capsules to equal required daily dosing | Store at 2°C to 8°C (36°F to 46°F). Store in original container. | |
| Placebo matching BMS-986165 oral capsule | Not applicable | IP | Blinded | Blister card containing 64 active (3 mg BMS-986165) and/or placebo capsules to equal required daily dosing | Store at 2°C to 8°C (36°F to 46°F). Store in original container. | |
| Any of the following: AZA, 6-MP, MTX, leflunomide, MMF; chloroquine, hydroxychloroquine, quinacrine | As prescribed | Non-IP | Open-label | As provided | As indicated | Subjects are to be receiving at least 1 of these at a stable dose for ≥ 8 weeks before the screening visit, throughout the screening period, and throughout the study. See Inclusion 3a (Section 5.1) for further information. Non-IP will not be provided by the Sponsor. |

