6.7.2 Existing Therapies for Systemic Lupus Erythematosus

All subjects will continue their existing SLE treatment(s) during the study (if the treatment complies with the eligibility criteria; [Section 5](#)). The dose and regimen of background SLE treatments must not change during study participation. Details of permissible therapies are as follows:

- At least 1 background agent as specified in Inclusion Criterion 3)a) ([Section 5.1](#)); use of more than 1 immunosuppressant in combination is NOT permitted.
- CS therapy with prednisone or equivalent as specified in Inclusion Criterion 3)b) ([Section 5.1](#)); see restrictions in [Section 6.7.1](#). CS tapering [REDACTED] are described in [Sections 6.7.3](#) [REDACTED]
- Chronic NSAID therapy as specified in Inclusion Criterion 3)c) ([Section 5.1](#))
- Stable preexisting topical CS therapy as specified in Inclusion 3)b) ([Section 5.1](#))

6.7.3 **Corticosteroid Tapering**

For subjects receiving prednisone or equivalent, the dose of CS must be stable for 2 weeks before the screening visit (signing of informed consent) and throughout the SP until randomization. Up to 30 mg/day prednisone or equivalent is permitted during the SP (and for the preceding 2 weeks). Rules for CS tapering are as follows:

- Tapering of CS may begin at any time after the first dose of IP on Day 1.
- For subjects receiving > 7.5 mg/day prednisone or equivalent, tapering must start by Week 8.
- For all subjects, the CS dose must be ≤ 7.5 mg prednisone or equivalent by Week 20 (if this is not possible, the subject will remain on treatment, but will be a nonresponder for analysis purposes).
- Investigators must assess the subject's suitability for CS taper at each visit (taper is not required to start until Week 8), and the last day for CS taper is the Week 20 visit.
- The CS dose must be tapered (beginning by Week 8 and continuing until the Week 20 visit) unless any of the following are observed:
 - New or worse BILAG or SLEDAI-2K activity for any of the following parameters: central nervous system, vasculitis, myositis, cardiorespiratory, gastrointestinal, ophthalmologic, renal, or thrombocytopenia
 - New or worsening hemolytic anemia
 - CLASI activity score ≥ 10
 - Active joint count of 8 or more joints with both tenderness AND swelling

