APPENDIX 6 COMMONLY USED CORTICOSTEROID EQUIVALENTS

| Medication | Dose Equivalence |
|--------------------|-------------------------|
| Prednisone | 20 mg |
| Cortisone | 100 mg |
| Hydrocortisone | 80 mg |
| Prednisolone | 20 mg |
| Methylprednisolone | 16 mg |
| Triamcinolone | 16 mg |
| Budesonide | 4 mg |
| Dexamethasone | 3 mg |
| Betamethasone | 2.4 mg |
| Deflazacort | 26 mg |

**APPENDIX 7 REQUIRED RECOVERY (WASHOUT) TIMES FOR SPECIFIC
MEDICATIONS PRIOR TO SCREENING**

| Medications | Discontinuation Prior to Signing Consent |
|--|---|
| Abatacept (CTLA4Ig) | 12 weeks |
| Acthar [®] gel (repository corticotropin injection) | 6 weeks |
| Adalimumab | 12 weeks |
| Alefacept | 8 weeks |
| AMG 623 | 12 weeks |
| Anakinra | 12 weeks |
| Apremilast | 4 weeks |
| Atacicept (TACI-Ig) | 48 weeks |
| Belimumab | 24 weeks |
| BIIB059 | 15 weeks |
| Certolizumab pegol | 24 weeks |
| Cyclophosphamide | 24 weeks |
| Cyclosporine | 4 weeks for systemic use (oral, IV, etc) |
| Danazol | 4 weeks |
| Dapsone | 4 weeks |
| Eculizumab | 12 weeks |
| Efalizumab | 8 weeks |
| Epratuzumab | 18 weeks |
| Etanercept | 4 weeks |
| Infliximab | 12 weeks |
| Intravenous globulin | 4 weeks |
| Leflunomide | 36 weeks |
| Lenalidomide with cholestyramine | 24 weeks |
| Lulizumab | 6 weeks |
| Lupuzor (IPP-201101) | 12 weeks |
| Memantine | 4 weeks |
| Natalizumab | 12 weeks |
| Obinutuzumab | 26 weeks |
| Ocrelizumab | 24 weeks |
| Ofatumumab | 26 weeks |
| Plasmapheresis | 24 weeks |

| Medications | Discontinuation Prior to Signing Consent |
|---|---|
| Retinoids (oral isotretinoin, and acitretin; topical retinoids are allowed) | 4 weeks |
| Rituximab | 24 weeks |
| Sifalimumab | 26 weeks |
| Sirolimus | 4 weeks |
| Sulfasalazine | 4 weeks |
| Tabalumab | 14 weeks |
| Tacrolimus | 4 weeks for systemic use (oral, IV, etc) |
| Thalidomide | 4 weeks |
| Tocilizumab | 12 weeks |
| Tofacitinib | 4 weeks |

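### The SAP's Appendix 7 non-responder trigger, as written, catches leflunomide, which the protocol permits as stable background therapy; no exemption is stated

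*SAP*

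**What the plan says.** **Leflunomide as permitted therapy.** Protocol 5.1, Inclusion Criterion 3a, requires background therapy and lists leflunomide among the allowed immunosuppressants; the dose must "remain stable until randomization and throughout study participation". Protocol Table 5 repeats the list of acceptable agents: "Any of the following: AZA, 6-MP, MTX, leflunomide, MMF; chloroquine, hydroxychloroquine, quinacrine". Protocol 6.7.2 adds: "The dose and regimen of background SLE treatments must not change during study participation".

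**Leflunomide as a listed washout drug.** Protocol Appendix 7, the table of discontinuation times before consent, has the row "Leflunomide | 36 weeks". Exclusion Criterion 3a in Protocol 5.2 excludes subjects for "inability to comply with discontinuation requirements listed in" that appendix.

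**The SAP rule.** The non-responder imputation (NRI) section of SAP 11.7.1 sets the observed response aside if any one of its conditions is met. One condition is "Subjects takes any medications included in protocol Appendix 7 between first dose date and efficacy assessment visit". Another, in the same list, names leflunomide as an immunosuppressant, counts only initiation or an increase over baseline, and allows a decrease, a stop, or a restart at the same or a lower dose.

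**Where the rule reaches.** SRI(4) at Week 48 is defined in the same way as at Week 32 (SAP 11.7.2.1). The Appendix 7 condition is repeated in the BICLA definition (11.7.2.2) and in the list of relevant deviations (SAP Appendix 5). In the joint-count mixed model (11.7.2.5), values at visits that meet the NRI criteria are set to missing.

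**The concern.** The two bullets give different answers for the same subject. Someone on a constant leflunomide dose passes the immunosuppressant bullet and fails the Appendix 7 bullet. The triggers are joined by a logical or, so passing one does not cancel failing the other. On the text, a subject is counted as a treatment failure for doing what Protocol 6.7.2 requires.

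At stake are a diluted estimate on the primary endpoint and an unclear responder definition. If the reading is chosen after unblinding, it becomes a post hoc decision about who is a responder.

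**Working it through.** **1. Is leflunomide the only overlap?** Inclusion Criterion 3a allows azathioprine, 6-mercaptopurine, methotrexate, leflunomide, mycophenolate, chloroquine, hydroxychloroquine and quinacrine. Of these, only leflunomide appears in the Appendix 7 table. A single named exemption therefore removes the whole conflict.

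**2. Apply the rule to one subject.** Take a subject on a constant leflunomide dose from before screening to Week 32, with an SRI(4) response observed.
- Immunosuppressant bullet: no initiation and no increase, so not triggered.
- Appendix 7 bullet: a listed drug was taken between first dose and the Week 32 visit, so triggered.
- Result: non-responder, whatever was observed.

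**3. Effect on the treatment difference.** Let f be the share of subjects caught by the rule. Background therapy is fixed before randomization, so f is expected to be the same in each arm. Assume that leflunomide users would otherwise respond like everyone else. Each arm's response rate is then multiplied by (1−f):

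difference = (p_active − p_placebo) × (1−f) = 20 × (1−f) points.

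The 20 points are the design difference in Protocol 9.1 and SAP 5.1. The documents do not give f, so the values below are assumptions.

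| Assumed f | Subjects out of 360 (360 × f) | Difference (points) |
|---|---|---|
| 0% | 0 | 20.0 |
| 1% | 3.6 | 19.8 |
| 2% | 7.2 | 19.6 |
| 5% | 18 | 19.0 |
| 10% | 36 | 18.0 |

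Each 1% of users costs 0.2 points. If the arms do not differ, both rates shrink by the same factor and remain equal, so the type I error rate is not inflated.

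**4. Can this be turned into lost power?** The stated figure is at least 84% power with 90 per arm. The placebo rate and testing scheme are redacted; the protocol's table of changes gives alpha 0.04 for the BID branch without saying whether it is one- or two-sided. With the normal approximation (pooled variance under the null) and a 20-point difference:
- each BID arm against placebo (90 vs 90), two-sided 0.04, assumed placebo rate 30% to 45%: 74.0% to 75.8%;
- the same comparison, one-sided 0.04, placebo 30%: 84.4%;
- the same comparison, two-sided 0.04, placebo 17%: 84.0%;
- both BID arms combined against placebo (180 vs 90), two-sided 0.04, placebo 30% to 45%: 85.8% to 87.0%.

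Several different set-ups land near 84%, so the stated figure can be neither confirmed nor refuted. Only the dilution in step 3 can be supported.

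**The case against.** **The intent is clear enough.** The medication triggers sit under a lead-in about prohibited medications. Protocol 9.3.1.2 likewise speaks of drugs that the protocol prohibits, and stable leflunomide is expressly allowed. Inclusion Criterion 3a refers to Appendix 7 for "Required discontinuation periods for other immunomodulatory drugs (eg, cyclosporine, tacrolimus, etc) or biologic drugs", which suggests drugs outside the permitted list. The appendix title concerns washout before screening. These points stand as evidence of intent. They do not repair the rule: the list under that lead-in defines what counts as prohibited, and it takes in the whole of Appendix 7 without exception.

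**The harm needs two readings of one table.** If Appendix 7 is read literally at entry, Exclusion Criterion 3a bars leflunomide users, and Protocol 5 states: "No subject will be randomized without confirmation of eligibility by CRS and the PRA medical monitor". Nobody would then be affected. A forced failure arises only if screening follows the permissive reading and the analysis follows the literal one. This stands as a limit on size. It is the same unresolved conflict, though, since Inclusion Criterion 3a and Table 5 admit these subjects.

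**The coding list may settle it.** SAP Appendix 5 promises a list of WHO Drug terms for the Appendix 7 drugs. It could leave out baseline leflunomide, but its content is not given.

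**Sensitivity analyses cover it.** Analyses #1 and #2 for SRI(4) do not apply the medication triggers, and the joint counts have a treatment-policy analysis. This limits the damage, but none of these replaces the primary analysis. For BICLA, the same kind of sensitivity analysis is planned, but the medication condition is part of the response definition, so it is unclear whether it would be lifted.

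**Conclusion.** The point holds as a defect in the wording of the primary-endpoint rule. It originates in the protocol, where Appendix 7 overlaps Inclusion Criterion 3a, and it passes into the SAP through an unqualified reference. As written, the rule forces a compliant leflunomide user to non-response for SRI(4) at Weeks 32 and 48 and for BICLA, and removes that subject's joint counts from the main model.

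The size is unknown and may be nil. If a share f is affected equally across arms, and leflunomide users otherwise respond like the rest, the difference is multiplied by (1−f).

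A reader might infer more in three ways, and the documents do not support them:
- *That the result would be biased in favour of the drug or the type I error inflated.* The trigger does not depend on arm, so its expected effect is dilution.
- *That leflunomide users will certainly be scored as failures.* That depends on whether any were randomized and on a coding list whose content is not given.
- *That a known number of users would push power below 84%.* With the BID arms combined, two-sided alpha 0.04 and placebo rates of 30% to 45%, the crossing point moves from about 6 to about 31 of 360 subjects with the placebo rate and variance formula chosen. If each BID arm is tested separately at that alpha, power is already below 84% with no leflunomide users at all. No break-even count can be defended.

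**What to change.** Before unblinding, add to the Appendix 7 condition in SAP 11.7.1, SAP 11.7.2.2 and SAP Appendix 5: *except leflunomide taken as baseline background therapy under Inclusion Criterion 3a at the same or a lower dose, including stopping and restarting at the same or a lower dose; such use is governed only by the initiation/increase bullet.* Carry the same exemption into the WHO Drug term list. Report the number of baseline leflunomide users per arm, so that readers can see whether the question mattered. The sponsor should also confirm in the protocol whether the 36-week washout applies to leflunomide taken under Inclusion Criterion 3a.

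The cost is one clause in three SAP places, one programming condition and a short protocol clarification. No new data are needed.
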